## **7.5.2 (Other) Secondary endpoints**

All other secondary analyses are of exploratory nature, no correction for multiple hypotheses testing will be made. All statistical tests and confidence intervals are two-sided with a significance level of  $\alpha=0.05$ .

### **7.5.2.1 Secondary/Tertiary cardiovascular endpoints**

For all secondary and tertiary CV endpoints that include time-to-event data the same models and testing procedures as the primary analysis (refer to [Section 7.4.1](#)) will be applied to compare the two treatment groups.

For time to first investigator reported heart failure (based on narrow SMQ cardiac failure) only frequencies and incidence rates will be provided. For time to first investigator reported heart failure (based on narrow SMQ cardiac failure) another analysis will be performed on the TS based on events occurring until + 7 days after permanent treatment discontinuation or date of last documented study visit, whichever comes first. Accordingly, patients without an event will be considered censored at the earliest of the date of last treatment stop + 7 days or last documented study visit.

The cumulative incidence function for time to first occurrence of each adjudicated CEC confirmed CV endpoint (except all-cause mortality), accounting for any death that is not part of the endpoint as a competing risk, will be provided. In addition a Cox's proportional hazards model will be applied to the competing risk.

For the secondary CV endpoints of occurrence of 4P-MACE and 3P-MACE sensitivity analysis on the TS, PPS and OS will be performed, considering events until earliest date of treatment stop + 30 days or date of last documented study visit. This covers the presentation of number and percentage of patients with an event.

For all adjudicated CV endpoints including all-cause mortality additional sensitivity analyses will be performed on the TS based on events occurring until + 30 days after permanent treatment discontinuation or date of last documented study visit, whichever comes first. Accordingly, patients without an event will be considered censored at the earliest of the date of last treatment stop + 30 days or last documented study visit.

- 7.5.2.2 Secondary/Tertiary diabetes related endpoints and UACR
- 7.5.2.2.1 Continuous diabetes related endpoints (FPG, HbA1c, total cholesterol, HDL cholesterol, LDL cholesterol, triglycerides, creatinine, urinary albumin, eGFR, weight and UACR)

Evaluation will be performed on standardized values. The analyses will be performed on the TS. Measurements will be assigned to weeks as described in [Section 6.7.3](#).

The absolute change from baseline will be calculated for each timepoint by subtracting the baseline value from the selected value at the respective time point.

#### Treatment-emergent evaluation

Patients with a baseline measurement and at least one on-treatment measurement will be included for analysis over time. Only values obtained until last permanent treatment stop will be considered. The assignment of values to be on-treatment is defined in [Table 6.7.2: 1](#).

In general, for the evaluation of HbA1c and FPG, for patients receiving rescue therapy all on-treatment efficacy measurement after the start of rescue therapy will not be used for analysis and hence set to missing (OC, LOCF). If a patient receives rescue therapy before the first available on-treatment measurement, this patient will not be included in the analysis, except for HbA1c LOCF analysis.

For total cholesterol, HDL cholesterol, LDL cholesterol, triglycerides, creatinine, urinary albumin, UACR, eGFR and weight values before and after rescue therapy intake will be considered (OC-ROC, LOCF-ROC).

In addition, analyses following the OC concept will be performed.

For the following parameters, only values obtained in the fasted state will be used for analyses: FPG, total cholesterol, HDL cholesterol, LDL cholesterol, triglycerides.

For UACR log10 transformed data will be used within the ANCOVA or respectively MMRM model, the results will be back-transformed to the original scale.

#### *Change from baseline to final visit on-treatment*

For the investigation of continuous diabetes related endpoints at the final visit, the following analysis of covariance (ANCOVA) model will be applied:

Efficacy endpoint as absolute change from baseline = overall mean + treatment + baseline measurement + random error

This model includes effects accounting for the following sources of variation: 'Treatment', and 'baseline'. 'Treatment' is a fixed classification effect and 'baseline' is a linear covariate. The random error is assumed to be normally distributed with mean 0 and variance  $\sigma^2$ .

The adjusted mean with SE for each treatment group, the adjusted mean difference with SE and the corresponding 95% CI will be reported.

Treatment-specific baseline will be investigated.

Descriptive statistics will be presented.

The analysis will be performed on OC and OC-ROC for HbA1c, FPG and ~~on OC-ROC~~ for Total cholesterol, HDL cholesterol, LDL cholesterol, Triglycerides, Creatinine, eGFR, urinary albumin, UACR and weight.

*Change from baseline over time – considering the design of the trial*

Only data up to the planned week that could theoretically be achieved by all patients will be included in this analysis. This time-point depends on the duration of the trial. If e.g. the trial would run for 7 years in total with 2 years for re-cruiting, the last patient randomised could theoretically only reach the visit at week 260. Then for all patients only the data up to planned week 260 will be included in this analysis.

*a) MMRM*

The change from baseline over time will be evaluated with a restricted maximum likelihood (REML) based mixed model repeated measures (MMRM) approach with the fixed, categorical effects of treatment, week, treatment-by-week interaction, with the continuous covariates of baseline and baseline-by-week interaction.

The baseline and the available longitudinal observations at each post baseline visit until last permanent treatment stop will be used for the analysis of these endpoints at each week.

The adjusted least-squares mean with standard error (SE) per treatment group, the mean difference with SE and 95% CI will be reported at all timepoints.

The average treatment difference over time will be provided in addition to the treatment difference per week for continuous endpoints.

An unstructured covariance structure will be used to model the within-patient errors.

In the event that this analysis cannot be applied for mathematical reasons or fails to converge, the AR(1) covariance structure will be employed. If this fails to converge, the compound symmetry (CS) covariance structure will be employed.

The Kenward-Roger approximation will be used to estimate the denominator degrees of freedom. Type III sums of squares will be used.

The analysis will be performed on OC and OC-ROC for HbA1c, FPG and for Total cholesterol, HDL cholesterol, LDL cholesterol, Triglycerides, Creatinine, eGFR, urinary albumin, UACR and weight.

*b) LOCF*

The last observation carried forward (LOCF) approach will be performed to conduct a sensitivity analysis. The change from baseline after replacement by LOCF will be evaluated with the analysis of covariance (ANCOVA) model as described above for every week.

The adjusted mean with SE for every treatment group, the adjusted mean difference with SE and 95% CI will be reported.

The analysis will be performed on LOCF and LOCF-ROC for HbA1c, FPG and for Total cholesterol, HDL cholesterol, LDL cholesterol, Triglycerides, Creatinine, eGFR, urinary albumin, UACR and weight.

*c) Descriptive statistics*

Descriptive statistics will be provided based on OC data and after LOCF imputation (OC, OC-ROC, LOCF, LOCF-ROC).

*Change from baseline over time*

MMRM analyses on OC and OC-ROC will be performed as described above. Simple descriptive statistics will be calculated for the change from baseline over time based on observed case data (OC and OC-ROC). All weeks will be considered.

*Sensitivity analysis for determination of influence of rescue medication and fasting*

For HbA1c and FPG and weight the above analyses considering the actual design of the trial applying MMRM analysis will be repeated including also data obtained after rescue therapy intake (OC-ROC and LOCF-ROC).

As stated above, approaches of OC and LOCF will also be performed for Total cholesterol, HDL cholesterol, LDL cholesterol, triglycerides, creatinine, eGFR, urinary albumin, UACR and weight.

For total cholesterol, HDL cholesterol, LDL cholesterol, triglycerides a sensitivity analysis using descriptive statistics will be performed for the change from baseline over time and at final visit based on OC-ROC, considering all values, obtained in fasted and non-fasted state.

Evaluation including all data independent of treatment

MMRM analyses on OC-ALL considering the actual design of the trial will be performed as described above for HbA1c, FPG and weight.

Descriptive statistics will be calculated for the change from baseline over time and to study end based on all observed data. All data obtained before and after intake of rescue therapy and independent of treatment stop will be considered (OC-ALL).

Descriptive statistics will also be provided after applying LOCF including all data obtained up to the planned week that could theoretically be achieved by all patients.

An ANCOVA will be performed for the change from baseline to final week per patient using the model as described above for HbA1c, FPG and weight.

Treatment-specific baseline will be investigated for the change from baseline to final week.

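### If the unstructured MMRM cannot be fitted, the AR(1) fallback with model-based errors can make the average-over-time treatment difference look too precise

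*SAP*

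**What the plan says.** SAP Section 7.5.2.2.1, part a) MMRM, models the change from baseline with treatment, week, their interaction, baseline and baseline-by-week. On the covariance it says: "An unstructured covariance structure will be used to model the within-patient errors". The first fallback is AR(1): "In the event that this analysis cannot be applied for mathematical reasons or fails to converge, the AR(1) covariance structure will be employed". The second applies only if AR(1) fails too: "If this fails to converge, the compound symmetry (CS) covariance structure will be employed". On inference: "The Kenward-Roger approximation will be used to estimate the denominator degrees of freedom". No empirical variance is mentioned, so model-based standard errors are the fair reading, although the SAP does not say so in words.

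The quantity at issue is a summary across visits: "The average treatment difference over time will be provided in addition to the treatment difference per week for continuous endpoints".

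The model is run in two settings. One is limited to weeks that every patient could in theory reach; the SAP's example is week 260. The other, under the later subheading on change from baseline over time, is not limited: "All weeks will be considered".

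SAP Section 7.5.2 sets the status of these endpoints: "All other secondary analyses are of exploratory nature, no correction for multiple hypotheses testing will be made".

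**The concern.** AR(1) by visit number lets the correlation decay geometrically. With a one-step correlation of 0.7, visits ten steps apart (about three years at 16-week spacing) would have correlation 0.7^10 = 0.03. If some patients run persistently higher than others on HbA1c or FPG, that is wrong. The standard error of an average over many visits depends heavily on exactly these long-lag correlations. Kenward-Roger corrects for small samples; it does not repair a wrong covariance structure.

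At stake is the interval around the average treatment difference, which would be too narrow. HbA1c change is a named trial objective (Protocol Section 2.2), so readers will look at this summary although it is exploratory.

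**Working it through.** The documents state no standard deviation, correlation or standard error for these models, so there is no figure of the plan's own to reproduce. The inputs are as follows.

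**From the documents**
- HbA1c: 16-week visits from Visit 6 (week 16), so 17 post-baseline visits to week 272.
- FPG: also Visits 3-5 (weeks 4, 8, 12), so 20 visits to week 272 and 30 to week 432 (Protocol Flow Chart).
- Lipids: Visits 6, 9, 12, 15, 18 and 21, so 6 visits to week 272 (Protocol Section 5.2.3.2).
- About 6,000 patients, so large-sample ratios apply.
- Two-sided 0.05 (SAP Section 7.5.2).

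**Assumed**
- Week 272 as the restricted horizon. It is the last scheduled visit within the 5.4-year follow-up of Protocol Section 7.6.
- Unit variance split into a persistent patient part *a* (20-40%), a decaying part *b* (30-50%, half-life *h* of 26-104 weeks) and noise *c* (30-40%), with *a* + *b* + *c* = 1.
- Complete data.

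**Formulas**
1. Raw covariance between weeks *s* and *t*: *a* + *b*·2^(−|t−s|/h), plus *c* when *s* = *t*. Condition this on the baseline value to get Σ.
2. Limiting AR(1) fit: V = σ²ρ^|i−j|, with σ² and ρ minimising log|V| + tr(V⁻¹Σ).
3. For the equal-weight average over *n* visits, w = (1/n, …, 1/n). The ratio of model-based to true SE is r = √(w′Vw / w′Σw). With complete data the estimate itself does not depend on V, and the group sizes cancel.
4. Understatement = 1 − r. Non-coverage of a 95% interval = 2(1 − Φ(1.96 r)).

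**A case that can be checked by hand.** Take a compound-symmetry truth with correlation 0.5, 16 visits and no baseline adjustment. The fitted ρ is 0.50.
- True variance of the mean: (1 + 15 × 0.5)/16 = 0.531.
- AR(1) variance of the mean: (1/16)[1.5/0.5 − 2(0.5)/(16 × 0.25)] = (3 − 0.25)/16 = 0.172.
- r = √(0.172/0.531) = 0.57, an understatement of 43%.
- Non-coverage: 2(1 − Φ(1.96 × 0.57)), about 26%.

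**Results under the assumed family, conditional on baseline**

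| Analysis | Visits | True/model SE | Understatement | Non-coverage |
|---|---|---|---|---|
| HbA1c to week 272 | 17 | 1.37-1.61 | 27-38% | 15-22% |
| FPG to week 272 | 20 | 1.41-1.69 | 29-41% | 16-25% |
| FPG, all weeks | 30 | 1.59-1.93 | 37-48% | 22-31% |
| Lipids to week 272 | 6 | 1.11-1.17 | 10-15% | 8-9% |

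**Wider structures, conditional on baseline, 16 visits, complete data**

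| Assumed truth | Understatement | Non-coverage |
|---|---|---|
| Compound symmetry | 44% | 27% |
| Random intercept and slope | 33-41% | 19-25% |
| Random intercept plus AR, with or without noise | 14-30% | 9-17% |
| AR plus noise, no random intercept | 16-28% | 10-16% |
| Pure AR(1) on the raw scale | 5% | 6% |

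With 40% monotone dropout, the ranges are 8-42% at 16 visits and 8-47% at 20. With 27 visits and complete data, the range is 5-56% (non-coverage 6-38%). Without baseline adjustment, a true AR(1) gives 0%.

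**Compound symmetry as the fallback, same truths.** The SE ratio is 1.00 with complete data and 0.89-1.00 with 40% dropout (non-coverage 5-8%).

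**Weekly differences.** Under AR(1) the weekly SE ratio is 1.00 for a compound-symmetry truth and otherwise errs in either direction (about 0.75 to 2.0). The consistent understatement is specific to the average.

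**The case against.** The case for leaving the text alone has real weight.

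- **The size is assumed.** A reader might infer that the fallback necessarily raises the error rate to some 17-32%. The documents do not support a fixed figure. They give no correlations, and realistic structures fall on both sides of that range. This stands.
- **Not every endpoint is hit alike.** A reader might also extend the headline size to all continuous diabetes endpoints. Lipids have 6 visits to week 272 and show about 10-15%. Similarly, AR(1) by visit number treats 4-week and 16-week gaps alike only for FPG, the one endpoint measured at Visits 3-5. This stands.
- **The fallback may never be used.** In the restricted analysis an unstructured matrix has n(n+1)/2 parameters: 136 at 16 visits and 210 at 20, against about 6,000 patients. Late-entry sparsity is excluded there by design, and nothing shows that the fit would fail. This stands for that analysis. In the all-weeks run, FPG has 30 visits and 465 parameters, and the last visits are reached only by the earliest patients still on treatment. Failure is more plausible there, though its chance cannot be judged.
- **The consequence is limited.** The SAP attaches an SE and 95% CI explicitly to the differences at each timepoint, and it names no test of the average. The defined endpoints are changes to Final Visit, analysed by ANCOVA without AR(1). So the harm is interval non-coverage in an exploratory summary. This also stands.

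None of this defends AR(1) with model-based errors as the first choice once the unstructured fit has failed. Under the structures examined, the SAP's own second fallback does clearly better for this estimand wherever correlation persists.

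**Conclusion.** The point holds in conditional form and is minor. If the unstructured fit fails, and if within-patient correlation persists over years, the stated rule gives too small an SE for the average treatment difference. Under a lasting patient component, the size is about 27-41% for HbA1c or FPG to week 272, up to about 48% for FPG over 30 visits, and about 10-15% for lipids. Over wider structures it is about 5-56%.

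This rests on assumed covariances, on reading the SAP as using model-based errors, and on the average being reported with an SE or interval. The primary and key secondary tests use Cox models and chi-square tests and are untouched.

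**What to change.** In SAP Section 7.5.2.2.1, part a) MMRM, add one sentence after the fallback order: *whenever a structured covariance replaces the unstructured one, the empirical (sandwich) variance will be used for standard errors and confidence intervals.* In large samples this restores coverage to about 95% by construction.

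Optionally, replace AR(1) as first fallback with a structure that allows persistent correlation: compound symmetry, already the second fallback, or its heterogeneous form. Heterogeneous Toeplitz is less attractive for FPG because, indexed by visit, it also ignores the unequal gaps.

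The cost is SAP wording and one procedure option. Kenward-Roger is not combined with the sandwich variance, which is immaterial at about 6,000 patients. The sandwich corrects the SE but not any bias in the estimate when a wrong covariance meets missing-at-random dropout, which is the reason to consider the optional change as well.

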#### Investigation of follow-up information obtained after treatment stop

A comparison of baseline, last value on-treatment and follow-up value will be performed for measures of SBP, DBP, pulse rate, FPG, eGFR.

A model including subgroup, subgroup-by-treatment interaction will be used.

#### 7.5.2.2.2 C-peptide, plasma pro-insulin and antibodies

Descriptive statistics of baseline values will be provided based on the TS and include geometric mean and geometric coefficient of variation. For C-peptide and pro-insulin only values obtained in fasted state will be considered.

#### 7.5.2.2.3 Binary diabetes related endpoints

The Chi-Square test is used to compare the two treatment groups and a logistic regression with factor treatment is performed to report the OR along with the 95% CI. The number and percentage of patients with response will be provided along with the 95% Wilson confidence intervals. The analysis will be performed on the TS.

#### 7.5.2.2.4 Time to and occurrence of antidiabetic rescue therapy

Time to first rescue therapy use among patients will be analysed by Kaplan-Meier estimates and compared using a log-rank test based on the TS.

The time to first rescue medication will be calculated as date of first intake of rescue therapy minus the date of first intake of randomised study drug plus one day.

For censoring refer to [Section 6.8](#).

The number and percentage of patients with rescue medication will be provided along with the 95% Wilson confidence intervals. The analysis will be performed on the TS.

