For incomplete date information the midpoint of the possible interval will be used. That means, if only the year is present the day and month will be imputed as 01 July, if year and month is present the day will be imputed as 15.

If the year is missing, the date will be considered missing.

If this leads to contradictions for the start or end date of a concomitant therapy (e.g. imputed end date before documented start date) a partial end date will be imputed as the end of the interval or a partial start date will be imputed as the start of the interval in the database to resolve this contradiction.

*Missing date of trial completion (=last contact or date of death)*

If the date is completely missing the following rules will be applied:

If a patient did not die (no corresponding vital status and/or adverse event information), the date of trial completion will be imputed by the last date the patient was known to be alive.

If a patient died and has not withdrawn consent, this date will be imputed by the date of death.

If a patient has withdrawn informed consent, this date will be imputed by the date of IC withdrawal.

If the date is incomplete with only month and year reported, the date will be imputed by the first day of this month.

Exception:

If the date last known to be alive, or respectively date of IC withdrawal is after the imputed date, the date of trial completion is to be imputed by this date.

If a patient died and has not withdrawn consent and the date of death is known, the date of trial completion will be imputed by the date of death.

Missing onset time of hypoglycaemia/ missing plasma concentration

If onset times are available for hypoglycaemic events then those events are only considered as on-treatment, if the onset is at or after the time of first drug administration. Missing onset times on the day of first drug administration will be imputed as the time of the start of drug administration and those hypoglycaemias will be counted as on treatment. Missing onset times on other days will be imputed as 0:00.

If a patient has multiple hypoglycaemic episodes and some of them have missing plasma glucose values, those with missing values will be excluded from the derivation of the minimum glucose level (worst episode).

Laboratory data

Missing safety laboratory data will not be replaced.

Laboratory data outside the limits of quantification

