#### *Time to first rescue medication (overall and protocol-defined)*

Patients without rescue medication intake that have prematurely and permanently stopped trial drug intake will be considered censored at their last documented study visit\* as described above.

Patients without rescue medication intake that have regularly completed trial drug intake until study end will be considered censored at their last treatment stop date.

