### *Time to first hypoglycaemia*

To keep the analysis of hypoglycaemia consistent with the overall AE analysis, a patient without an event will be considered censored at the date of last trial drug intake + 7 days or date of death, if earlier. For further details refer to [Section 7.8.1.6](#).

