#### 7.8.1.6 Analysis of hypoglycaemic events

All symptomatic hypoglycaemic events, all asymptomatic events with glucose levels less than 3.0 mmol/L (or less than 54 mg/dL) and all asymptomatic hypoglycaemic events that are considered as adverse events by the investigator have to be recorded as an adverse event with additional information to assess the intensity of the hypoglycaemic event.

For asymptomatic hypoglycaemia with a measured plasma glucose concentration  $\geq 3.0$  and  $\leq 3.9$  mmol/L ( $\geq 54$  and  $\leq 70$  mg/dL), if not considered as adverse event, the plasma glucose levels values will be recorded in the CRF.

Analyses on hypoglycaemic events will be performed on the TS.

Different tables will be shown for (i) patients with investigator defined asymptomatic or symptomatic hypoglycaemia reported on the CRF, and (ii) patients with (by the investigator) confirmed hypoglycaemic adverse events and (iii) asymptomatic hypoglycaemia.

The number of patients with investigator defined hypoglycaemia (adverse events) will be tabulated by treatment group. In addition, the number of patients with different characteristics of hypoglycaemic events, including severity, symptoms, glucose level, minimum glucose level of the worst episode, number of episodes per patient as well as time to first hypoglycaemic episode will be presented.

The number of patients with hypoglycaemic events and investigator defined hypoglycaemia adverse events will be shown by age group and by use of rescue medication (yes, no).

Time to the onset of the first hypoglycaemia and first hypoglycaemia adverse event will be analysed by Kaplan-Meier estimates. A log rank test will be performed. For the details on censoring refer to [Section 6.8](#) and [7.8.1.3.2](#).

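### Kaplan-Meier with deaths censored overstates the cumulative probability of first rescue and first hypoglycaemia; the SAP plans cumulative incidence for its adjudicated CV endpoints but not for these two

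*SAP*

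**What the plan says.** - **Estimators.** For rescue, SAP 7.5.2.2.4: "Time to first rescue therapy use among patients will be analysed by Kaplan-Meier estimates and compared using a log-rank test based on the TS". For hypoglycaemia, SAP 7.8.1.6: "Time to the onset of the first hypoglycaemia and first hypoglycaemia adverse event will be analysed by Kaplan-Meier estimates", followed by a log-rank test.
- **Censoring, hypoglycaemia (SAP 6.8.3).** "a patient without an event will be considered censored at the date of last trial drug intake + 7 days or date of death", whichever is earlier. Death is named.
- **Censoring, rescue (SAP 6.8.3).** There are two categories. "Patients without rescue medication intake that have prematurely and permanently stopped trial drug intake will be considered censored at their last documented study visit". "Patients without rescue medication intake that have regularly completed trial drug intake until study end will be considered censored at their last treatment stop date". Death is not named. A patient who dies without rescue fits only the first category. The last documented visit takes in the trial completion date, which the missing-date rules in 6.6 take to be the last contact or the death date.
- **Competing risks elsewhere.** SAP 7.4.2.2 (3P-MACE) and 7.5.1 (4P-MACE) add a cumulative incidence with non-CV death as the competing event. SAP 7.5.2.1 does so for each adjudicated CV endpoint other than all-cause mortality, "accounting for any death that is not part of the endpoint as a competing risk, will be provided". No such curve is planned for rescue or hypoglycaemia.
- **Other absolute summaries.** For rescue, SAP 7.5.2.2.4: "The number and percentage of patients with rescue medication will be provided along with the 95% Wilson confidence intervals". For hypoglycaemia, 7.8.1.6 gives patient counts, and 7.8.1.3.2 gives incidence rates, rate ratios and rate differences.
- **Status.** SAP 7.5.2 calls the other secondary analyses exploratory; SAP 7.8.1 calls the adverse event analyses descriptive.

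**The concern.** Kaplan-Meier handles a censored patient as one who stays exposed to the same future risk as those still followed. That is reasonable for the end of the study. It does not describe a patient who has died, who will never start rescue or have a first hypoglycaemia. With deaths censored, one minus Kaplan-Meier answers a hypothetical question (the probability if nobody died) and lies above the real-world probability whenever deaths occur. The direction needs no assumption.

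The point matters more for these endpoints than for many others because they are likely to be frequent. At a fixed death rate over 6 years, the excess grows with the event hazard up to roughly 0.30 per year. Follow-up is long (Protocol 7.6: 2 years of accrual plus 5.4 years) and patients are at high CV risk and up to 85 years old. Hypoglycaemia incidence is a named objective in Protocol 2.2, and readers tend to take absolute risks from such curves.

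**Working it through.** **Inputs from the documents.** Protocol synopsis: about 3000 patients per arm. Protocol 7.6: 2 years of accrual and 5.4 years of follow-up, so about 5.4 to 7.4 years per patient. This follow-up can be checked: 6000 patients, 1.8% events per year, 1.5% loss per year and uniform accrual give 628 expected events against the 631 planned. There is no stated rescue or hypoglycaemia probability to reproduce.

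**Assumed inputs.** The documents give no rescue rate, no any-hypoglycaemia rate and no all-cause death rate. All rates below are assumptions.

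**Formulas.** With constant hazards λ (event) and μ (death), over T years and N patients per arm:
- one minus Kaplan-Meier = 1 − exp(−λT)
- cumulative incidence = λ/(λ+μ) × [1 − exp(−(λ+μ)T)]
- Greenwood SE = exp(−λT) × √{ λ/[N(λ+μ)] × [exp((λ+μ)T) − 1] }, ignoring loss and administrative censoring before T

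**Rescue, T = 6, N = 3000.** For λ = 0.12 and μ = 0.015: 1 − exp(−0.72) = 51.3%; (0.12/0.135) × [1 − exp(−0.81)] = 0.889 × 0.555 = 49.3%.

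| λ | μ | 1 − KM | Cumulative incidence | Excess (points) | SE (points) | Excess/SE |
|---|---|---|---|---|---|---|
| 0.05 | 0.005 | 25.9% | 25.6% | 0.37 | 0.81 | 0.45 |
| 0.05 | 0.010 | 25.9% | 25.2% | 0.7 | 0.81 | 0.9 |
| 0.12 | 0.015 | 51.3% | 49.3% | 2.0 | 0.94 | 2.1 |
| 0.16 | 0.025 | 61.7% | 58.0% | 3.7 | 0.93 | 4.0 |

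**Wider grid.** With T from 4 to 8.3 years, rescue 2% to 20% per year and death 0.5% to 3% per year (annual percentages p converted to hazards by −ln(1−p)), the excess runs from 0.08 to 7.0 points.

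**Between-arm difference in rescue, equal death rates of 1.0% to 2.5% per year, T = 6.**
- λ = 0.10 against 0.12: 6.2 points by Kaplan-Meier, 5.9 to 6.1 by cumulative incidence; shift 0.14 to 0.33 point (0.10 to 0.25 SE of the difference).
- λ = 0.12 against 0.16: 10.4 points against 9.9 to 10.2; shift 0.20 to 0.49 point (at most 0.37 SE).
- λ = 0.05 against 0.16, a very large contrast: shift 0.8 to 2.0 points.

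**Hypoglycaemia.** Assume hazard 0.15 in year 1 then 0.06, or 0.20 then 0.08; on-treatment death 0.8% to 2.0% per year; drug stop 5% per year as censoring. One minus Kaplan-Meier at 6 years is 36% or 45%, and the excess due to death is 0.65 to 1.9 points (0.7 to 1.9 SE). At a constant 0.02 per year with death 0.8%, it is 0.26 point (0.41 SE).

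**Drug stop compared with death.** At 6.4 years with hypoglycaemia at 10% per year, counting death at 1% to 2% per year as competing lowers the probability by 1.4 to 2.7 points. Counting drug stop at 4% to 6% per year instead lowers it by 5.3 to 7.7 points.

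**The case against.** The strongest reply is that little depends on these curves. The analyses are exploratory or descriptive, outside the testing hierarchy, and the log-rank test remains a valid comparison of cause-specific hazards. Neither 7.5.2.2.4 nor 7.8.1.6 lists Kaplan-Meier rates at fixed times, as 7.4.1.1 does for the primary endpoint. Absolute occurrence is also reported in other ways: a percentage with Wilson intervals for rescue, and counts and incidence rates for hypoglycaemia. Harm arises only if someone reads one minus Kaplan-Meier as a real-world probability. All of this stands, and it keeps the point minor. It does not remove it: the crude percentage mixes patients with about 5.4 to 7.4 years of follow-up, an incidence rate is not a probability, and the curve is the natural place to read off a risk at a given year.

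A second reply also stands. For the primary endpoint the SAP keeps Kaplan-Meier (7.4.1.1) and adds cumulative incidence as a sensitivity display (7.4.2.2). That precedent supports adding a curve here. It does not support removing Kaplan-Meier.

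A reader might infer more than the documents support:
- *That the plan states probabilities which are wrong by a known amount.* It states none, and the size depends wholly on assumed rates.
- *That the excess always exceeds half a standard error.* It does not at lower rates (0.45 SE for rescue at 0.05 with death 0.5% per year; 0.41 SE for hypoglycaemia at 0.02). The Protocol's benefit-risk section describes linagliptin's hypoglycaemia risk as low.
- *That the treatment comparison is materially distorted.* For modest contrasts the shift is a few tenths of a point.

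**Conclusion.** The point holds as a minor one about absolute risks. Both endpoints are displayed by Kaplan-Meier with deaths censored, and one minus Kaplan-Meier then lies above the real-world cumulative probability. The SAP already plans the remedy for its adjudicated CV endpoints.

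For rescue, the excess is about 0.7 to 3.7 points per arm if the rescue hazard is 0.05 to 0.16 per year, death is 1.0% to 2.5% per year, hazards are constant and the horizon is 6 years. Outside those assumptions it can be about 0.1 to 7 points. The between-arm difference typically shifts by about 0.1 to 0.5 point for modest contrasts with equal death rates, and by more only for very large contrasts. Log-rank results, alpha, power and every confirmatory conclusion are unchanged.

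For hypoglycaemia, correcting for death alone would not give the share of all patients who ever have an episode. Follow-up ends 7 days after the last dose, so the curve stays an on-treatment one, and under the assumed rates drug stop matters more than death.

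**What to change.** 1. In SAP 7.5.2.2.4 and 7.8.1.6, add the Aalen-Johansen cumulative incidence by arm, with death before the event, within each endpoint's own follow-up window, as the competing event. Take any quoted absolute probability from this estimate.
2. Keep the Kaplan-Meier curve and the log-rank test, described as the cause-specific comparison.
3. In SAP 6.8.3, state how a patient who dies without rescue is handled, including the date used.
4. Label the hypoglycaemia curves as on-treatment, with patients censored 7 days after drug stop.

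The cost is a few SAP sentences and a small programming addition, since cumulative incidence programs are already needed for the CV endpoints. The displayed percentages will be slightly lower.
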